**Analysis Plan for Aim 2 (BMZ-exposed subjects in usual care group vs intervention group):**

Cord blood C-peptide levels will be compared between randomized arms (usual care vs. screening/treatment after BMZ) using a linear model, controlling for gestational age at randomization. We will estimate the mean difference between groups along with a 95% confidence interval. Similar models will be used to compare 2° metabolic measurements such as cord blood cortisol, insulin-like growth factor, and leptin levels between BMZ-exposed usual care vs. BMZ-exposed intervention group. Metabolic and hormonal analytes will be correlated with our exploratory outcomes: neonatal hypoglycemia (defined as neonatal glucose < 40mg/dL within 48 hours of birth), NICU admission, and NICU stay  $\geq$  72 hours.

If the 2 groups show a difference in the 1° outcome, interactions will be evaluated using linear regression models and subgroup analyses conducted to determine whether the effect differs across particular subgroups of patients. In particular we will assess subgroups defined by gestational age (dichotomized at 36 wks), interval from BMZ exposure to delivery (dichotomized at 3 days), maternal obesity (defined as BMI  $\geq$  30 kg/m^2 at time of delivery), race/ethnicity, and expected indication for late preterm delivery at trial entry (preterm premature rupture of membranes vs. preterm labor vs. obstetrical/medical indication). We will conduct 2° analyses to examine neonatal sex (male vs. female) on the 1° outcome.

We will use linear regression models to assess the association between randomization arm, time since first dose of BMZ until delivery, doses of BMZ received, and the interactions of the latter two with each of the study arm approaches (usual care vs. screening/treatment). We will estimate the association between time interval to delivery and number of BMZ doses separately in each study arm and compare the associations between arms.

Loss to follow-up will be defined as the inability to ascertain whether the neonate was born alive and if born alive umbilical cord blood not collected. Those defined as lost to follow-up will not be included in the primary analysis. It is expected that the loss to follow-up rate will be very low, less than 10 percent. However, a sensitivity analysis will be performed including patients lost to follow-up with “worst case” assumptions regarding their outcome to determine whether the results are robust.

In general, analyses of data will be conducted to address the primary and secondary research questions of the trial. All hypothesis tests that are observed to be *not* statistically significant will be reported as being inconclusive.

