### 3.6. Randomization Method

The randomization sequence will be prepared in a permuted block design, stratified by study site and gestational age at trial entry (34 weeks 0 days – 34 weeks 6 days and 35 weeks 0 days – 36 weeks 5 days) to assure balance between the two groups with respect to anticipated differences within the patient populations and possible differences in other aspects of patient management. The study statistician will create the randomization scheme, and assignments will be centrally assigned using the Research Electronic Data Capture (REDCap) application. Enrolled subjects will be randomized in a 1:1 ratio to usual care (no maternal glucose screening or treatment) or to study intervention (regular maternal glucose screening and treatment).

The randomization sequence will be generated by a statistician and uploaded into REDCap. This sequence will be unknown by any other study personnel and will be unable to be accessed in REDCap by anyone other than the statistician. As such there is full concealment of randomization group until a patient is screened, meets all eligibility criteria, signs the consent form, and the randomization function in REDCap is utilized to place the subject in the control or intervention group. Once the subject is assigned to a group, this randomization cannot be undone.

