**Table 4. Power for Sample Size = 144 ( $\alpha=0.05$ )**

---

As shown in Table 4, this sample size provides reasonable power to detect a clinically meaningful difference in C-peptide levels between the intervention and usual care groups after BMZ exposure. This calculation was performed using a range of expected

Power (%) if 10% loss to follow-up (n=130)	Power (%) for subgroup if 70% deliver in 3 days (n=100)	Mean difference in C-peptide level (mcg/L)	Standard deviation	Sample size needed
95	85	0.5	0.75	84 (42/group)
95	90	1	1.5	98 (49/group)
90	80	1.5	2.5	90 (45/group)
98	90	1.5	2	78 (39/group)

primary outcomes based on previously reported values (normal C-peptide 0.6-1.0mcg/L, 95th percentile C-peptide 1.77mcg/L, C-peptide after antenatal BMZ exposure 2.85mcg/L) under conservative scenarios. Further, this sample size will be sufficient to detect differences in cortisol and insulin-like growth factor between these groups with more than 80-90% power based on previously reported values and the same assumptions above.

In addition to these 144 women enrolled prospectively, we will have access to 75 umbilical cord blood samples from the MOTOR trial. With this available sample size based on the same conservative scenarios in Table 4, we will have ≥80% power to compare C-peptide levels between unexposed controls and women exposed to BMZ who are randomized to usual care.

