## 5.2. Interim Analysis

The Data and Safety Monitoring Board meets monthly; however, a formal interim analyses for overwhelming efficacy is planned after 50% of recruitment is completed (n=75). For the planned interim analysis, a formal detailed statistical report will be written by [name], Biostatistician including protocol adherence, the primary outcome, and adverse events reported as well as center performance in terms of recruitment, data quality, loss to follow-up and protocol violations.

The main statistical issue relevant to interim analysis is the problem of performing multiple tests of significance on accumulating data. A number of procedures have been developed to handle this situation. For this trial, the group sequential method will be used to control the type I error with the Lan-DeMets spending function and the O’Brien-Fleming type boundary. Assuming that the analysis is conducted at precisely 50%, this implies that the alphas to be used will be 0.003 and 0.049 at the interim and final analyses, respectively. However, this should not preclude the Data and Safety Monitoring Board recommending termination earlier if there is evidence of harm. Pre-specified stopping rules for safety will be developed.

It is recognized that any decision to terminate the study would not be reached solely on statistical grounds but on a number of complex clinical and statistical considerations.

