### 1.1. Analysis Plan

A detailed Statistical Analysis Plan will be written before the first subject is enrolled into this study. The following is a summary of the proposed plan. [name] will be responsible for statistical computations.

All statistical analyses will be based upon the total cohort of patients randomized into the trial. Although data on some patients may be missing, all relevant data available from each patient will be employed in the analyses. Patients will be included in the treatment group to which they were randomly assigned regardless of treatment actually received (intention to treat).

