##### 4.2. Recruitment and Data Collection Period

In the MFMU ALPS study, there were 24,133 women who were screened for participation at 17 sites over a total of 53 months. Of these, 2,831 were eligible and underwent randomization. Specific enrollment data was reviewed for the 4 sites participating in this study. As shown below, enrollment increased over time.

ALPS Enrollment	UNC	Northwestern	Total
Oct 2010 – Dec 2010	3 patients (1pt/mo)	1 patient (0.3pt/mo)	4 patients (1.3pt/mo)
Jan 2011 – Dec 2011	46 patients (3.8pt/mo)	31 patients (2.6pt/mo)	77 patients (6.4pt/mo)
Jan 2012 – Oct 2012	74 patients (7.4pt/mo)	59 patients (5.9pt/mo)	133 patients (13.3pt/mo)

Assuming a similar consent rate since there are no major safety concerns yields approximately 150 subjects per year. Therefore it would be reasonable to assume that approximately 144 patients could be comfortably enrolled over an 18-month period. This translates to an enrollment rate of approximately 8 patients per month.

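### The Aim 2 primary model omits study site, a stratification factor; if site predicts C-peptide, the analysis is mildly conservative

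*Combined protocol and SAP*

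**What the plan says.** Section 3.6 (Randomization Method) describes a "permuted block design, stratified by study site and gestational age at trial entry". The purpose given is "to assure balance between the two groups with respect to anticipated differences within the patient populations", together with possible differences in other aspects of management.

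The Analysis Plan for Aim 2 compares cord-blood C-peptide between arms "using a linear model, controlling for gestational age at randomization", reports the mean difference with a 95% confidence interval, and uses similar models for cortisol, insulin-like growth factor and leptin. Site appears neither there nor in the general Analysis Plan text.

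That general text calls itself a summary and says: "A detailed Statistical Analysis Plan will be written before the first subject is enrolled into this study". The detailed plan is not among the documents.

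On power, section 5.1 says "this sample size provides reasonable power to detect a clinically meaningful difference in C-peptide levels". Its bold row in Table 4 (difference 1 mcg/L, SD 1.5) states 95% power at n=130.

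**The concern.** One of the two stratification factors is carried into the primary model and the other is not, and no reason is given. The protocol stratifies by site because it expects sites to differ in patients and care. Insulin treatment in the intervention arm also follows each institution's existing protocol (section 3.3). So the plan itself gives some reason to think site could be related to the outcome.

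Blocking within site balances the arms within each site, so site differences largely cancel out of the arm comparison. An analysis that ignores site still counts those differences as noise. The reported interval is then wider, and the p-value larger, than the design warrants. This has some practical weight because the plan reports every non-significant test as inconclusive.

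**Working it through.** **Inputs.** 144 women randomised 1:1, 130 evaluable after 10% loss (section 5.1, Table 4). Two Table 4 rows: difference 1, SD 1.5, stated power 95%; and difference 1.5, SD 2.5, stated power 90%. Alpha 0.05, taken as two-sided. The share of C-peptide variance explained by site, ρ, is not in the documents; 0, 5, 10 and 20% are assumed. Table 4's SD is read as the total SD.

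**Table 4 first.** The standard error is 2·SD/√n = 2 × 1.5/√130 = 0.263 mcg/L. The two-sided normal approximation gives 96.7% power for the bold row (stated 95%) and 92.8% for the 1.5/2.5 row (stated 90%). Both stated figures are a little below the computed ones.

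**Formulas.**
- Standard error reported by the model without site: 2·SD/√n.
- True standard error under site-stratified allocation: 2·SD·√(1−ρ)/√n.
- Overstatement: 1/√(1−ρ).
- Actual type I error without site: 2·[1 − Φ(1.96/√(1−ρ))].
- Power without site: Φ[(difference − t × model SE)/true SE], with t = 1.979.
- Power with site: noncentral t with noncentrality difference/true SE.

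**Example, bold row, ρ = 10%.** Model SE 0.2631; true SE 0.2631 × √0.9 = 0.2496. Without site: (1 − 1.979 × 0.2631)/0.2496 = 1.92, so power is 97.3%. With site: noncentrality 1/0.2496 = 4.01, so power is 97.8%.

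| Site share ρ | SE overstated | Actual type I error | Power 1/1.5, without v with site | Power 1.5/2.5, without v with site |
|---|---|---|---|---|
| 0% | 0% | 5.0% | no difference | no difference |
| 5% | 2.6% | 4.4% | 96.9 v 97.2% | 93.0 v 93.6% |
| 10% | 5.4% | 3.9% | 97.3 v 97.8% | 93.6 v 94.7% |
| 20% | 11.8% | 2.8% | 97.9 v 98.8% | 94.7 v 96.7% |

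In the bold row the 95% interval half-width is 0.52 mcg/L without site, against 0.51, 0.49 and 0.47 with site at ρ = 5, 10 and 20%.

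**Simulation checks** (blocks of 4 assumed; 2 or 4 sites).
- At n=130 and nominal 5%, type I error without site was about 3.9% at ρ = 10% and 3.0% at 20%. With site it stayed between 4.7 and 5.2% throughout.
- If the true difference were 0.75 rather than 1 mcg/L (SD 1.5), power was 81–82% without site v 84% with it at ρ = 10%, and 83% v 88–89% at 20%.
- With 144 randomised, 14 lost at random and the final alpha of 0.049, the gain at ρ = 20% was 1.2 points (1/1.5 row) and 2.3–2.5 points (1.5/2.5 row), slightly above the closed form because some blocks are incomplete. Without site, power never fell below 96.2% and 92.0% in the two rows.

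**The case against.** **The text is only a summary.** The detailed SAP may already list site, and that cannot be checked here. This stands as a limit on what can be claimed. It does not change the model as written, which names one stratification factor and not the other.

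**The larger scenarios are demanding.** With two equal sites and SD 1.5, the site means must differ by 2 × 1.5 × √ρ, which is 0.67, 0.95 and 1.34 mcg/L at ρ = 5, 10 and 20%. The 10% case therefore needs a site difference about as large as the planned treatment effect of 1 mcg/L, and the 20% case a larger one. Nothing in the documents points to differences of that size. At 2% the effect is negligible: standard error 0.263 v 0.260, type I error about 4.8%. This stands, and it is why the lower end of the range deserves more weight.

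**The power reassurance depends on reading Table 4's SD as total.** If it were the within-site SD, the model SE at ρ = 20% in the bold row would be 0.2631/√0.8 = 0.294 and the true SE 0.263. Power without site would be Φ[(1 − 1.96 × 0.294)/0.263] = 94.6% against the stated 95%. The same steps give about 89% against 90% in the 1.5/2.5 row. This also stands, but the shortfall is about a point or less and arises at the extreme of the range.

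**A slightly conservative model is a legitimate choice.** It is, if made deliberately. The plan gives no reason, and adjusting costs almost nothing even when site has no effect.

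**Conclusion.** The concern holds as a minor point of precision and specification. The stated Aim 2 model leaves out a factor the trial randomises by. The effect depends entirely on how much C-peptide variance site explains, which the documents do not give. At 5 to 10%, the standard error is 2.6 to 5.4% too large, and the power given up is 0.3 to 0.5 points in the 1/1.5 row and 0.6 to 1.1 points in the 1.5/2.5 row. At 20% the loss is 0.9 and 2.0 points; at zero there is none.

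The treatment estimate is unbiased and type I error is at or below nominal in every case. With Table 4's SD read as total, the stated power at n=130 is still met without site in both rows examined. Block size and the number of sites were assumed in the simulations and barely affect the result.

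**What to change.** State in the SAP that the Aim 2 primary model contains arm, study site as a fixed effect, and gestational age at randomisation, and say whether gestational age enters as the randomisation stratum or as a continuous term. Use the same model for the secondary cord-blood analytes. Section 5.2 says "a formal interim analyses for overwhelming efficacy is planned after 50% of recruitment is completed" but specifies no model for it, so name the same one there. If site is to be left out, give the reason.

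Confirm the number of sites when writing this line. Section 4.2 (Recruitment and Data Collection Period) says "Specific enrollment data was reviewed for the 4 sites participating in this study", but the table beneath it shows two. The section on participating centres was not in the text available for this review and may settle the matter.

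The cost is one line and 1 degree of freedom with two sites or 3 with four. No new data are needed, because site is already recorded for randomisation. It should be settled before outcome data are seen, so that the choice cannot look data-driven.

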### 4.3. Baseline Procedures

In addition to information collected for eligibility, project gestational age, and project EDD determination, the following information will be obtained at randomization from a patient interview followed by a review of her medical record:

- Demographic and anthropometric information: age, race, pre-pregnancy weight, current weight, and height
- Social history: marital status, years of education, alcohol use, tobacco use, and other maternal drug use
- Medical/surgical history: pre-existing maternal medical problems such as cardiac disease, asthma, infections, thyroid disorder
- Obstetrical history including value of diabetes testing in this pregnancy (1hr 50g glucose screen and 3hr 100g oral glucose tolerance test) and outcome of all prior pregnancies
- Current pregnancy complications including membrane rupture, preterm labor, bleeding, hypertensive disorders of pregnancy, oligohydramnios, non-reassuring fetal status, etc.

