#### **Analysis Plan for Aim 1 (MOTOR subjects not exposed to BMZ vs BMZ-exposed subjects in usual care group):**

Umbilical cord blood C-peptide levels will be compared between controls not exposed to BMZ from the MOTOR study and BMZ-exposed subjects prospectively randomized to usual care, using a linear model. We will estimate

the mean difference between groups along with a 95% confidence interval. For this comparison between controls not exposed to BMZ from the MOTOR study and BMZ-exposed subjects prospectively randomized to usual care, we will adjust for the following potential confounding factors: periodontal treatment in the MOTOR trial, gestational age at delivery, maternal BMI on admission, and fetal gender. Unfortunately we will not be able to accurately ascertain who among the women prospectively enrolled in the randomized trial has periodontal disease, and thus we will not be able to adjust for periodontitis in our analysis. Periodontitis as an unmeasured confounder is unlikely to bias the analysis of our primary outcome, umbilical cord blood C-peptide, but could bias the analysis of other secondary outcomes which are related to inflammation, such as cortisol. We will plan to state this as a limitation of the study in the final manuscript and interpret the results accordingly. A planned subgroup analysis will be performed comparing the BMZ-unexposed controls to women who were randomized to usual care and delivered within 3 days of BMZ exposure. Other 2° outcomes including umbilical cord blood cortisol, insulin-like growth factor, and leptin levels will be tested in similarly. We will not adjust for multiple comparisons, but will present results for all comparisons regardless of “significance.”

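### The Aim 2 C-peptide model adjusts only for gestational age; adding the glucose-screen value and BMI, both already collected at randomization, could give a modest gain in precision

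*Combined protocol and SAP*

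**What the plan says.** The Analysis Plan for Aim 2 compares cord C-peptide between usual care and screening/treatment "using a linear model, controlling for gestational age at randomization". It says that similar models will serve for cortisol, insulin-like growth factor and leptin.

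Section 4.3 (Baseline Procedures) states that "the following information will be obtained at randomization from a patient interview followed by a review of her medical record". Its list includes "Demographic and anthropometric information: age, race, pre-pregnancy weight, current weight, and height" and "Obstetrical history including value of diabetes testing in this pregnancy (1hr 50g glucose screen and 3hr 100g oral glucose tolerance test". The screen value appears in no analysis that the plan describes.

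In Aim 2, BMI enters only as a subgroup factor, "maternal obesity (defined as BMI" of at least 30 kg/m² at delivery, and only if the primary outcome differs between arms. In Aim 1, the C-peptide comparison with the MOTOR controls is adjusted for "periodontal treatment in the MOTOR trial, gestational age at delivery, maternal BMI on admission, and fetal gender".

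The Analysis Plan describes itself as a summary and says: "A detailed Statistical Analysis Plan will be written before the first subject is enrolled into this study".

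**The concern.** Cord C-peptide has no pre-treatment value, so the usual way of gaining precision, adjusting for the baseline outcome, is not available. The nearest substitute is a baseline variable on the causal path. Section 2.3 gives that path: betamethasone raises maternal insulin resistance and glucose, glucose crosses the placenta, and the fetal pancreas responds with insulin. A woman's glucose tolerance in this pregnancy and her BMI are plausible markers of how strongly she will respond. Neither can be changed by the allocated strategy. Betamethasone may precede randomization by up to 6 hours, but that applies to both arms and cannot alter an earlier screen result.

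If these variables predict C-peptide, leaving them out keeps explainable variation in the residual and widens the primary 95% confidence interval. The width matters here because the plan will report every non-significant test as inconclusive.

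**Working it through.** **Inputs from the documents.** 144 women randomized 1:1. With 10% loss, 144 × 0.9 = 129.6, which Table 4 takes as 130 (65 per group). The subgroup delivering within 3 days is taken as 100 (50 per group). Alpha is 0.05, assumed two-sided because the plan does not say. The standardized effects in Table 4 are 0.5/0.75 = 0.67, 1/1.5 = 0.67, 1.5/2.5 = 0.60 and 1.5/2 = 0.75, so the smallest is 0.60.

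**Input not in the documents.** R², the share of C-peptide variance that screen value and BMI explain beyond arm and gestational age. It is assumed here, from 0 to 20%.

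**Reproducing Table 4.** Two-sample noncentral t, with noncentrality d × √(n/2) for n per group.
- Bolded row (difference 1, SD 1.5): 96.5% at 65 per group (95% stated) and 91.0% at 50 per group (90% stated). At the stated 49 per group, power is 90.4%. This row reproduces.
- 0.60 SD row (difference 1.5, SD 2.5): 92.4% at 65 per group (90% stated) and 84.4% at 50 per group (80% stated). The stated 80% matches the power at that row's needed sample size of 45 per group (80.4%), not at 50. The recomputed 92.4% and 84.4% are the starting values below.

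**Effect of adjustment.** The residual SD is multiplied by √(1 − R²), so:
- SE ratio = √(1 − R²)
- equivalent gain in women = 1/(1 − R²) − 1
- effect size for power = 0.60/√(1 − R²), with three further degrees of freedom charged for the screen value, BMI and a missing-value indicator.

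For example, at R² = 0.10 the SE ratio is √0.90 = 0.949, the equivalent gain is 1/0.90 − 1 = 11%, and the effect size is 0.60/0.949 = 0.632.

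| Assumed R² | Fall in SE | Equivalent extra women | Power, 0.6 SD, 65/group | Power, 0.6 SD, 50/group |
|---|---|---|---|---|
| 0 | 0% | 0% | 92.4% | 84.4% |
| 2% | 1% | 2% | 92.9% | 85.1% |
| 5% | 2.5% | 5% | 93.6% | 86.1% |
| 10% | 5% | 11% | 94.7% | 87.9% |
| 20% | 11% | 25% | 96.7% | 91.3% |

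**Interval width.** In the bolded row (SD 1.5, 65 per group) the 95% half-width is 1.96 × 1.5 × √(2/65) = 0.516 mcg/L unadjusted. At R² = 10% it is 0.516 × 0.949 = 0.489, and at 20% it is 0.516 × 0.894 = 0.461.

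**Break-even.** The planned model has three terms (intercept, arm, gestational age). Adding k terms pays for itself once R² exceeds roughly k/(N − 3).
- Two covariates: 2/127 = 1.6% at 130 women and 2/97 = 2.1% at 100.
- With the missing-value indicator as a third term: 3/127 = 2.4% and 3/97 = 3.1%.

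Below those values the adjustment gains nothing and costs a trivial amount.

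**The case against.** **This is a choice, not an error.** That stands. The arms are randomized, so the planned model is unbiased and its interval valid. A reader might infer that a chance imbalance in glucose tolerance or BMI is a further problem. It is not, because that variability is already part of the planned standard error.

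**The gain is assumed and may be close to nothing.** This largely stands. The documents give no correlation. Section 3.4.3 excludes pregestational and gestational diabetes, which narrows the range of screen values. Section 2.3 says that nearly all non-diabetic women exceed 140 mg/dL after betamethasone, so the hyperglycemia may be mainly steroid-driven. Insulin in one arm could weaken the link there too. The plan also does not say how many women will have a 50 g value.

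**Power is already high.** This stands for the full cohort: at 0.6 SD the gain is about 1 to 2 points for R² of 5 to 10%. Larger gains could be shown for effects below 0.6 SD, but Table 4 contains none. The 3-day subgroup gains more, but it is not the primary comparison.

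**Aim 1 adjusts for BMI and fetal sex, so Aim 2 is inconsistent.** A reader might infer this, but it does not follow. The Aim 1 covariates are there to control confounding in a non-randomized comparison with stored samples. Randomization removes that need in Aim 2.

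**A detailed SAP is still to come.** This does not answer the point, because the summary already states the primary model and its covariate. It does mean that there is a natural place to make the change.

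**Site has a stronger claim.** Section 3.6 stratifies by site and gestational age, and the Aim 2 model omits site. That is a fair but separate observation, and it does not bear on whether these two covariates are worth adding.

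**Conclusion.** The point holds as an inexpensive improvement in precision. The Aim 2 model as written uses one baseline covariate, while two plausible predictors of C-peptide are collected before the allocated strategy starts and go unused in that model.

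Across assumed R² values of 0 to 20%, power at 0.6 SD rises by 0 to about 4 points in the full cohort (92.4% to 96.7%) and by 0 to about 7 points in the 3-day subgroup (84.4% to 91.3%). The lower part of the range is the more cautious expectation, given the exclusion of diabetic women. The result rests on the assumed R², two-sided alpha of 0.05, the planned 65 or 50 evaluable women per group, and screen values being available for most women.

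The documents do not support a reading that the primary estimate is biased, that its interval is invalid, or that the trial is underpowered for want of these covariates.

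**What to change.** In the detailed SAP, before any outcome data are seen by arm, specify the Aim 2 primary model as cord C-peptide on arm, gestational age at randomization, the 1-hour 50 g screen value and BMI at randomization (from current weight and height). Enter the screen value and BMI as continuous terms. For women without a screen value, use mean imputation plus a missing-value indicator, so that no woman with a cord sample is dropped. Use the same covariates in the matching cortisol, insulin-like growth factor and leptin models.

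The cost is SAP wording and about three degrees of freedom out of roughly 128. No new data, visits or sample size are needed. If many screen values are missing, the gain shrinks, so the SAP should also say that the number missing will be reported by arm.
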